Study Protocol and Statistical Analysis Plan

Protocol: Planning for the Care you Want
Rev. 9/18/2017

PI: [name]

NCT: 02320123

The University of Texas Southwestern Medical Center at Dallas
Institutional Review Board

[figure not shown]
Title: Planning for the Care You Want

Funding Source: AHRQ 1R24HS022418-01 (PI: [name]), Palliative Care Research Cooperative Group (PI: [name])

- 1. Introduction and Purpose:** The goal of this patient-centered project is to develop and pilot test a multicomponent intervention to increase intent to discuss end-of-life (EOL) care options among African American (AA) patients with life-limiting illness. This will be accomplished through the following specific aims, which are to: 1) Develop and refine a culturally sensitive intervention to increase knowledge about, reduce barriers, and promote intention to discuss EOL care options among AA patients hospitalized with advanced illness who are ≥ 55 years of age; and 2) Test the feasibility and acceptability of a theory-based, multi-component pilot program that will identify older AA patients hospitalized with advanced illness via the e-EOL algorithm and then deploy a culturally sensitive, patient-centered intervention to change knowledge and barriers about and intent to discuss EOL care options.

A separate aim is also included in the overall study, which has been funded by the Agency for Healthcare Research and Quality (AHRQ) and the Palliative Care Research Cooperative Group. The entire 3-aim study is Project 2 in the AHRQ-funded UT Southwestern Center of Patient-Centered Outcomes and Research. The first aim mentioned above, serves as a precursor to the aims described in this protocol. This aim, which uses applied medical informatics and chart review methods to develop an EMR-enabled (e-EOL) algorithm to identify patients hospitalized with advanced breast, lung, and colorectal cancer appropriate for EOL care counseling was approved in IRB submission STU 122010-078. It will be referred to at times in this protocol. Figure 1 shows the flow of the chronological flow of the entire proposal.

Figure 1

For the purposes of this IRB protocol, Aims 2 and 3 of the overall project will be referred to as Aim 1 and Aim 2 moving forward.

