B. A lay health advisor (LHA) will be recruited from the community to provide counsel about EOL care to patients who will receive the intervention. The LHA will undergo training in how to provide culturally sensitive EOL care for AAs via the APPEAL (A Progressive Palliative Care Educational Curriculum for the Care of AAs at Life's End) Curriculum created at Duke University, the Respecting Choices® Advance Care Planning curriculum, or other appropriate training program depending on availability. After training, the LHA will participate in in-service work with the Parkland Palliative Care Team and the PI.

Aim 2:

We will use the e-EOL algorithm (IRB #: STU 122010-078) to identify AA patients hospitalized at Parkland who have advanced breast, lung, and colorectal cancer to identify potentially eligible candidates for the intervention (See Aim 1 eligibility criteria); however, if sufficient numbers are not identified, patients with other advanced cancers will also be considered. Once eligibility is confirmed the PI or her designee (research assistant, coordinator, or LHA) will introduce the study to the patient, and obtain informed consent. Each patient will be asked to identify a primary caregiver who may be able to participate in the intervention. Of note, if a caregiver cannot be identified, is not eligible, or cannot participate in the intervention for other reasons (scheduling difficulties, etc.), the patient will still be allowed to participate. Caregivers are not required to participate in the intervention (i.e. watch the DVD segments), though it will be encouraged. The PI or her designee (research assistant, coordinator, or LHA) will contact the patient to confirm participation in the study, and arrange a time to meet to conduct the intervention. We anticipate that 48 patients (and their caregivers if available) will be enrolled in the study (16 for each type of cancer). We plan to conduct a small, pilot randomized controlled trial with up to 24 patients (and their caregivers if available) in the intervention arm, and up to 24 patients (and their caregivers if available) in a usual-care control group. The PI will randomize every other eligible patient (and caregiver if available) to the usual-care control group.

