9. Recruitment Methods and Consenting Process: Aim 1: The PI and research assistant will work with the attending physicians in the Parkland Palliative Care Clinic, Amelia Court Geriatrics Clinic, the Parkland inpatient Geriatrics and General Internal Medicine services, and researchers at the Simons Cancer Center to identify eligible candidates for semi-structured interviews and focus groups. Information will also be obtained for patient's caregivers, and they will be contacted by phone and regular mail to assess their interest in participation.

Palliative Care providers will be recruited via professional contacts. Providers will be approached via email and phone to assess their interest in participating in the focus group.

AA Religious leaders will be recruited from the African American Pastors Coalition and/or local AA churches. They will be approached by email (if available) and phone to assess their interest in participating in the study.

Aim 2: Patient participants will be recruited via development of a computerized algorithm using EMR data to identify hospitalized patients with advanced illness appropriate for EOL care discussion according to national guidelines. Development and validation of this algorithm is currently in process and has already received IRB approval (STU 122010-078: Evaluation of Racial Differences in Palliative and End-of-Life Care among Persons with Life-Limiting Illness). The algorithm will run once every day to flag potentially eligible candidates using an IT protocol used successfully in previous research at Parkland. The PI or her designee (research assistant or research coordinator) will contact the attending physicians of those identified by the algorithm to confirm eligibility and get permission to introduce the study to those patients. Creation of the algorithm is actually Aim 1 of an AHRQ-funded study that includes all three aims; consequently, the algorithm will be complete enough to use for recruitment in Aim 2 described here.

The PI or her designee (research assistant, research coordinator, or LHA) will contact each patient's primary caregiver by phone to confirm their participation in the study.

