The PI will use descriptive statistics to characterize study participants and proportion of intervention elements and follow-up assessments completed. The specificity and positive predictive value of the e-EOL algorithm operating in real world practice will be assessed using methods described for Aim 1 with physician chart review as the criterion standard. Acceptability and feasibility process data will be tallied. The main decision making outcome will be *change in the stage of intent to discuss EOL care options* from baseline through all follow-up intervals. Movement to an adjacent stage is a 1 point change. The PI will assess several aspects of stage change based on the proportion of patients at each time interval showing: 1) *any stage pro/regression*, and 2) *full progression to the action stage of discussion EOL care options*. Mean and range of progression at each interval will also be reported. The proportions above and means for *persistent change* will also be defined as the difference between baseline and 6 months (or 3 months if no 6 month contact or patient deceased). The PI will similarly examine pre- and post-intervention changes over time in knowledge, attitudes, and beliefs about EOL care and prognosis, decisional conflict, and QOL using non-parametric tests among the intervention group versus controls. Pre-specified subgroup analyses will stratify change in outcomes by: condition, mistrust, and spirituality. To achieve sensitivity of around 50% (with 10% confidence intervals, e.g. CI: 40% to 60%) in the outpatient algorithm, the PI will need to review 150 charts of patients diagnosed with metastatic (Stage III or IV) breast, lung and colorectal cancer (75 "test positive" and 75 "test negative" cases). The controlled pilot study in Aim 3 is designed to establish: feasibility, acceptability, detect preliminary efficacy signals (changes in behavioral intent, knowledge, attitudes, beliefs, decisional conflict), and generate point/variance estimates to be used to in power calculations for a future fully-powered RCT. The PI proposes a small pilot RCT that will include 24 patient-caregiver pairs in each arm (intervention versus a usual care control group). This will yield greater than 80% power to detect a large intervention effect defined as an absolute difference in desired primary outcome of 40% (across a range of different point estimates), and between 60-70% power to detect a more modest absolute difference of 30% between the two groups (across a range of point estimates). To ensure the ability to recruit the additional patient-caregiver pairs for the study, the PI will extend the enrollment period from 15 months to 18 months. Parkland Hospital providers care for more than 900 breast, lung and colon cancer patients per year, and roughly 40% are African American; consequently the PI believes that she will be able to successfully enroll this number of participants within an 18-month timeframe.

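### Does the 150-chart validation sample, split 75/75 by algorithm result, support the stated 40% to 60% interval for sensitivity?

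*Combined protocol and SAP*

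**What the plan says.** The Statistical Analysis Plan gives the target as "To achieve sensitivity of around 50% (with 10% confidence intervals, e.g. CI: 40% to 60%) in the outpatient algorithm" and continues that "the PI will need to review 150 charts of patients diagnosed with metastatic (Stage III or IV) breast, lung and colorectal cancer", with 75 test-positive and 75 test-negative cases. It states no confidence level, no expected share of criterion-positive patients, no expected share flagged and no formula.

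Earlier in the same section, the specificity and positive predictive value of the algorithm in practice "will be assessed using methods described for Aim 1 with physician chart review as the criterion standard". The section calls the pilot trial Aim 3, so it is using the numbering of the overall grant. On that numbering Aim 1 is the algorithm work, which section 1 (Introduction and Purpose) says "was approved in IRB submission STU 122010-078". Section 9 (Recruitment Methods and Consenting Process) adds: "Development and validation of this algorithm is currently in process and has already received IRB approval".

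Section 1 describes the algorithm's purpose as "to identify patients hospitalized with advanced breast, lung, and colorectal cancer appropriate for EOL care counseling", and section 3 (Concise Summary of Project, Aim 2) uses it "to identify AA patients hospitalized at Parkland who have advanced breast, lung, and colorectal cancer". Under section 9, the attending physicians of flagged patients are contacted "to confirm eligibility and get permission to introduce the study to those patients".

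**The concern.** The sampling and the target are conditioned on different things. Sampling by test result fixes the denominators of the positive and negative predictive values. Sensitivity has the criterion-positive patients as its denominator, and a 75/75 split by test result leaves their number to chance. To recover sensitivity, the two strata must be weighted by the flagged and unflagged shares of the source population. The width of the interval then depends on how common criterion-positive patients are, so 40% to 60% does not follow from 150 charts alone.

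Two things could be at stake. The interval could be wider than stated. And if the 150 charts were pooled without weights, sensitivity would be overstated and specificity understated whenever fewer than half of source patients are flagged. Physician confirmation does not guard against low sensitivity, because it reaches only flagged patients. The reference to an outpatient algorithm also sits oddly with the hospitalised patients described in sections 1 and 3.

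**Working it through.** **Inputs from the Statistical Analysis Plan:** sensitivity about 0.50, interval 0.40 to 0.60, 75 flagged and 75 unflagged charts.

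**Inputs assumed, because the documents give none:** confidence level (95%, with 90% as the alternative); π, the criterion-positive share of source patients; q, the flagged share; and PPV and NPV, the predictive values.

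**1. Can the figure be reproduced as a single proportion?** n = z² × 0.25 / 0.10².
- 95%: 1.960² × 25 = 96.04, so 97 criterion-positive charts.
- 90%: 1.645² × 25 = 67.6, so 68.
- With n = 75 the half-width is 11.3 points at 95% and 9.5 points at 90%. The exact 90% interval at 50% is 40.0% to 60.0%.

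So 75 criterion-positive charts would yield the plan's figure at 90% confidence. That may be where it came from, although the text says test-positive. The total of 150 cannot be derived from the stated inputs alone.

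**2. The design as written.** Sensitivity = q·PPV / [q·PPV + (1−q)(1−NPV)]. With q known,

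Var(logit) = (1/PPV − 1)/75 + (1/(1−NPV) − 1)/75.

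At sensitivity 0.5, PPV = π/(2q) and 1−NPV = π/(2(1−q)). The sum of their reciprocals is 2q/π + 2(1−q)/π = 2/π, so q cancels:

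Var(logit) = (2/π − 2)/75.

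**3. Threshold.** An upper limit of 0.60 needs z × √Var = ln(0.60/0.40) = 0.4055. Solving, π = 2 / (2 + 75 × (0.4055/z)²), which is 38.4% at 95% and 30.5% at 90%. On the untransformed scale the values are 39.0% and 31.1%. Because PPV cannot exceed 1, q must be at least π/2, about 19% or 15%.

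**4. Range of π, sensitivity 50%:**

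| π | 95% interval | 90% interval |
|---|---|---|
| 20% | 34.5–65.5% | 36.9–63.1% |
| 30% | 38.0–62.0% | 39.9–60.1% |
| 38.4% | 40.0–60.0% | 41.6–58.4% |
| 50% | 42.1–57.9% | 43.3–56.7% |
| 60% | 43.5–56.5% | 44.5–55.5% |

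Simulation with 200,000 samples at π = 38.4% put the central 95% of estimates at about 41% to 61% (specificity 0.80) and 41% to 62% (specificity 0.95), in line with the formula.

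**5. If q is itself estimated.** With q estimated from 300 to 900 source patients, the threshold rises to about 41–51% at 95%, or 32–40% at 90%.

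**6. Pooling without weights.** At true sensitivity 50%, the unweighted value is PPV/(PPV + 1 − NPV) = 1 − q. For an assumed q = 20% and PPV = 0.6, 1 − NPV = 0.24/1.6 = 0.15. Apparent sensitivity is then 0.60/0.75 = 80%. Apparent specificity is 0.85/(0.85 + 0.40) = 68%, against a true 0.68/0.76 = 89%. At q = 50% there is no bias. The plan does not propose this analysis.

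**The case for a change.** The strongest case for a change is that the plan makes an unconditional precision statement that in fact depends on an unstated quantity. The thresholds in steps 2 and 3 were re-derived independently with the same result. They are lenient, because they treat the flagged share as known. If fewer than about 19% of source patients are flagged, the 95% target cannot be met with this split at any PPV. The pointer to methods described elsewhere is attached to specificity and positive predictive value, not to the sensitivity sentence. Stating the weighting and the confidence level would cost only a line of text.

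The algebra stands, and so does the observation that the assumption is not written beside the figure. The step from there to a defect does not. No document gives π, q or PPV, so there is no ground for placing the study below the threshold rather than above it. The interval also moves little in the middle of the range: at 30% or 50% criterion-positive, each 95% limit is only about 2 points from the stated one. The pooling bias belongs to an analysis that nobody has proposed. To draw 75 flagged and 75 unflagged charts, the source patients must first be run through the algorithm, so the counts needed for weighting should be to hand, and weighting is the usual way to analyse such a sample. The missing details may also be in the separate submission, which these documents do not include.

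**Conclusion.** No change to the plan follows. The sentence omits a planning assumption; it is not shown to contain an error. Read literally, with sensitivity exactly 50% and the flagged share known, 150 charts reach 40% to 60% if at least about 38% of source patients are criterion-positive at 95% confidence, or about 31% at 90%. The requirement is higher if the flagged share is estimated. If 75 criterion-positive charts were meant, the figure is right at 90% confidence without any such condition. The documents do not settle which reading applies, and on neither is the chart count shown to be too small.

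The consequence is limited to the description of the algorithm. No decision rule in the documents uses the sensitivity interval. The assessment of the algorithm in practice names specificity and positive predictive value. The power statement and outcome comparisons of the randomised pilot do not depend on this interval. The outpatient wording may refer to another phase of the algorithm work; it raises a question of terms and does not alter any calculation.

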The LHA will meet with eligible patients and available caregivers in the intervention arm and assist them in watching the developed DVD segments. Afterward, the LHA will answer questions and provide additional information. They will tailor the discussion to the patient's values, preferences, concerns, and clinical circumstances. The patients who are enrolled in the usual care arm will not receive the intervention.

The primary process outcome tested will be the feasibility and acceptability of the intervention. Feasibility success will be measured by the number and rates of patients/caregivers who complete the intervention and follow-up interviews. The primary decision-making outcome is change in intent to discuss EOL care options based on the Transtheoretical Stages of Change Model (i.e., pre-contemplation, contemplation, preparation, and action). Secondary outcomes measured will include: 1) knowledge of prognosis and EOL care options; 2) quality of life, which will be measured by the McGill QOL Questionnaire, a well-validated 20 item scale developed to measure quality of life at the end of life; 3) health care utilization, such as outpatient visits, ER visits, hospitalizations, use of hospice services; and 4) date and place of death if applicable. Other patient and treatment variables will also be collected. The study variables, data sources, time frame of measurement, and references for the validated instruments are outlined in Table 2.

Table 2. Study Variables, Data Sources, and Time Frame Measurements

Variable	Source	Index Admit	Time Frame		
			1 month	3 months	6 months
Sociodemographics, clinical, treatment data	Chart review	X			
Knowledge of prognosis, EOL care options	Interview	X	X	X	
Feasibility and acceptability of the intervention	Interview	X	X	X	
Mistrust and spirituality	Interview	X	X	X	
Intent to consider EOL care options	Interview	X	X	X	X
Quality of life	Interview	X	X	X	
Healthcare and EOL utilization	Interview, chart	X	X	X	X

4. Study Procedures:

For Aim 1:

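### The stated power holds only if all, or nearly all, of the 24 patients per arm are evaluable, but 24 is also the enrolment maximum and the plan foresees deaths and missed contacts

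*Combined protocol and SAP*

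**What the plan says.** The Statistical Analysis Plan sets the size of the Aim 2 pilot: "The PI proposes a small pilot RCT that will include 24 patient-caregiver pairs in each arm". It then gives the power: "This will yield greater than 80% power to detect a large intervention effect defined as an absolute difference in desired primary outcome of 40" per cent, and "between 60-70% power to detect a more modest absolute difference of 30% between the two groups". Both figures are said to hold over a range of point estimates, which is not given.

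Section 3 (Concise Summary of Project, Aim 2) sets the enrolment as "up to 24 patients (and their caregivers if available) in the intervention arm", with the same limit for usual care and 48 patients in all.

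Several places show that losses are expected:
- Section 4 (Study Procedures, Aim 2) runs telephone interviews at 1, 3 and 6 months after discharge, where applicable.
- Section 3 lists among the secondary outcomes "date and place of death if applicable".
- Section 3 also makes completion of follow-up a feasibility measure: "Feasibility success will be measured by the number and rates of patients/caregivers who complete the intervention and follow-up interviews".
- The Statistical Analysis Plan lets the persistent-change measure fall back to an earlier contact ("or 3 months if no 6 month contact or patient deceased").

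Stage change is analysed "based on the proportion of patients at each time interval showing" progression or regression, or arrival at the action stage. The number available for analysis can therefore differ from one interval to the next.

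**The concern.** The power is computed at the largest number that can be enrolled, so it has no margin. If the deaths and missed contacts that the plan provides for occur, fewer than 24 per arm will contribute at 1, 3 or 6 months, and the stated power will not be the power at that interval. The power statement names no interval, loss rate, test, alpha, sidedness or control-rate range, so a reader cannot work out how much loss it can bear.

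This is the plan's only statement of how well the pilot can detect a preliminary efficacy signal. If it is too favourable, a pilot result showing no difference could be given more weight than the evaluable numbers justify.

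**Working it through.** **Inputs from the documents.** 24 per arm, 1:1; differences of 40 and 30 points; stated power above 80% and 60-70% (Statistical Analysis Plan). Maximum of 24 per arm (section 3, Aim 2).

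**Assumptions, since the documents are silent.** Alpha 0.05. Control rates in 5-point steps, 10-50% for 40 points and 10-60% for 30 points. The patient is the unit, and lost patients leave the denominator.

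**Formulas.** With n evaluable per arm, rates p1 and p2, difference d = p2 - p1, p̄ = (p1 + p2)/2, and S = √[(p1(1-p1) + p2(1-p2))/n]:
- Pooled, two-sided: power = Φ{[d - 1.96·√(2p̄(1-p̄)/n)] / S}
- Unpooled, two-sided: power = Φ{d/S - 1.96}
- Uncorrected chi-square and Fisher: sum of the binomial probabilities of all outcome pairs in which the test rejects.

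**Step 1: reproduce the plan's figure at 24.** For 40 points the least favourable control rate is 30% (30% against 70%).
- Pooled: √(0.5/24) = 0.1443 and S = √(0.42/24) = 0.1323. Then (0.40 - 1.96 × 0.1443)/0.1323 = 0.885, and Φ = 81.2%.
- Unpooled: 0.40/0.1323 - 1.96 = 1.064, and Φ = 85.6%.

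Both exceed 80%, as stated.

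**Step 2: remove patients.**
- Pooled at 23: (0.40 - 1.96 × 0.1474)/0.1351 = 0.822, giving 79.4%. One loss per arm takes the minimum below 80%.
- Unpooled at 21: 0.868, giving 80.7%. At 20: 0.800, giving 78.8%. Three losses per arm are bearable and four are not.
- Two-sided chi-square and one-sided Fisher: 80.9% at 23 and 77.8% at 22. One loss per arm is bearable.

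**Step 3: all bases that roughly reproduce both stated figures at 24 per arm (power in %).**

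| Basis (alpha 0.05) | 40 points, n=24 | 30 points, n=24 | Losses per arm with 40-point power still above 80% | 40-point minimum, n=20 | 30 points, n=20 |
|---|---|---|---|---|---|
| Two-sided pooled | 81-88 | 55-68 | 0 | 73 | 47-60 |
| Two-sided chi-square | 84-90 | 59-71 | 1 | 71 | 45-62 |
| One-sided Fisher | 84-90 | 59-71 | 1 | 71 | 45-62 |
| Two-sided unpooled | 86-92 | 59-73 | 3 | 79 | 51-65 |

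**Step 4: a larger loss, for illustration.** An assumed 25% loss leaves 24 × 0.75 = 18 per arm. The two-sided pooled formula then gives 68-77% for 40 points and 43-55% for 30 points. I use this formula because exact power does not fall smoothly with n: the chi-square minimum is 71.3% at 20 but 73.7% at 18, purely from discreteness.

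**The case against.** **The figures are not miscalculated.** This stands. With 24 evaluable per arm they can be reproduced. A reader might infer an arithmetic error, or that more patients must be enrolled. The documents support neither, since they give no loss rate and no basis that contradicts the figures.

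**A more generous basis may have been used.** The one-sided pooled formula stays above 80% down to 19 per arm, which is 5 losses. At 24 per arm, however, it gives 68-79% for 30 points, mostly above the stated 60-70%. With about 20 evaluable it does fit (83-89% and 60-72%), which would mean that an allowance is already built in. The text cannot exclude this, but it attaches the figures to 24 per arm and mentions no such allowance. Nor can a reader infer that a two-sided test was meant: at 24 per arm, one-sided Fisher and two-sided chi-square fit almost identically.

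**The 3-month fallback covers losses.** It does so in part. It softens losses after 3 months for persistent change only, it gives no rule for a patient with neither contact, and it does not apply to the analyses at each interval.

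**Lost patients need not leave the denominator.** This is true, because the plan names no analysis set. Counting them as not progressed would keep 24 per arm but shrink the difference. With an equal 25% loss, 40 × 0.75 = 30 points, for which the plan itself states only 60-70%. Replacement of lost patients is not excluded either, but it is not mentioned, and 24 is the stated maximum.

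**It is a pilot.** This stands and limits the weight. Feasibility and acceptability come first, the loss rate is one of the things to be learned, and power below 80% for 30 points is already disclosed.

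**Conclusion.** The power statement is wrong as written, in this limited sense: it says that 24 pairs per arm will give the stated power, and that power is not delivered once the foreseen losses occur. Among the bases that roughly match both stated figures at 24 per arm, 40-point power stays above 80% at every control rate considered only with at most 0 losses per arm (two-sided pooled), 1 (two-sided chi-square or one-sided Fisher) or 3 (two-sided unpooled). Larger losses cost roughly 7 to 12 points of minimum 40-point power at 20 per arm (for example 85.6 - 78.8 = 6.8 unpooled and 83.6 - 71.3 = 12.3 chi-square).

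These sizes rest on the assumed alpha, tests and control rates and on complete-case counting. The loss levels are illustrations, not predictions. Severity is minor: no design feature or outcome depends on the answer, and the main aim is feasibility.

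**What to change.** Keep 24 per arm and keep the present figures, but label them as applying to 24 evaluable patients per arm. State the basis actually used, and add one line by the same method. Suggested wording, with the team's own values:

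*These figures assume 24 evaluable patients per arm ([test], [one/two]-sided alpha [x], control rates [a-b]%, [1/3/6]-month interval). With [m] evaluable per arm, the number expected at that interval after deaths and missed contacts, power by the same method is [y]% for a 40-point and [z]% for a 30-point difference.*

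If the present figures already allow for losses, or if lost patients will be counted as not progressed, the same line should say so.

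The cost is a change of wording in the Statistical Analysis Plan and, in most cases, a less favourable stated power. It needs no extra patients and changes no outcome definition.
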